## 7. Sample Size and Accrual

### 7.1 Primary Outcome Sample Size Calculations

Our proposed HEAL sites report an overall mortality rate of 14%. Using three large sites that participated in the phase II study (UCSF, Wash U, CNMC) we can also estimate the rates of neurodevelopmental impairment: death = 14%; moderate-severe impairment = 18%; mild impairment = 17%; and normal = 51%. Therefore, we anticipate a control primary outcome rate of 49% (death or NDI).

#### 7.1.1 Non-human Data Informing Treatment Effect Size

A recent study with nonhuman primates (*Macaca nemestrina*) compared animals experiencing 15-18 minutes of umbilical cord occlusion that were then treated with either saline (n=14), therapeutic hypothermia (n=9), or therapeutic hypothermia and multiple doses of Epo. Among animals treated with saline 8/14 = 57% died or had NDI. Among animals treated with hypothermia (HT) alone 7/9 = 78% died or had NDI, while among animals treated with hypothermia and Epo (HT+Epo) only 5/12 = 42% were observed to die or have NDI. Results from Figure 2 of Traudt et al. show the number of animals in each outcome category by treatment group. These data suggest a risk ratio of 0.53 (95% CI: 0.25, 1.14) comparing HT+Epo to HT alone, and a risk ratio of 0.73 (95% CI: 0.32, 1.64) comparing HT+Epo versus saline. Therefore, animal data support an Epo effect that optimistically corresponds to a 50% reduction, and that is conservatively associated with a 27% reduction in the primary outcome rate.

#### 7.1.2 Phase I Data Informing Treatment Outcome Rates

Given that the primary outcome is based on a 22-26 month assessment (and for extenuating circumstances such as COVID-19 restrictions, up to 36 months of age) we can rely on a recently completed long-term follow-up from a phase I study in which 24 cooled infants were given multiple doses of Epo ranging from 250U/kg to 2500U/kg. At 22-26 months of age n=22 subjects were followed, and 0/22 subjects died, 1/22 had moderate-severe NDI, and 6/22 had mild NDI. This study suggests an overall primary outcome rate of 7/22 = 31.8% (exact confidence interval = 14%-55%) for our planned intervention group. We recognize that the dosing of Epo was not optimized in the phase I trial, and our proposed study will use multiple doses of 1000U/kg for all subjects which has been shown to yield plasma concentrations observed to be neuroprotective in animal studies.

**Table 3. Distribution of outcomes in previous studies**

	NEATO Epo (n=22)	NEATO Placebo (n=25)	Bayley III Cognitive	Trivedi et al. (submitted)
Injury Severity			Mean	Std. Dev.
None (0)	8 (36%)	3 (12%)	96	(8)
Mild (1-11)	13 (59%)	11(44%)	100	(13)
Moderate (12-32)	1 (5%)	6 (24%)	85	(18)
Severe (>32)	0 (0%)	5 (20%)	76	(19)
Predicted Bayley III (Mean (SD))	97.9 (11.7)	91.1(15.2)		
Predicted %<90	25.1%	47.1%		
Predicted death/NDI	34.1%	54.5%		

### 7.1.3 Phase II Data Informing Treatment Outcome Rates

In our phase II NEATO trial, a total of n=50 subjects were randomized to Epo (n=24) or placebo (n=26). We find substantial differences in the MRI injury severity distribution with 95% of Epo treated subjects having no injury or mild injury as compared to only 56% of control subjects. Using a recently submitted study from Trivedi, et al., we can then link the MRI injury severity category to expected Bayley III Cognitive scores at 24 months. Using our NEATO data and Trivedi's data we calculate a predicted mean (SD) of 97.9 (11.7) among Epo treated subjects, and a mean (SD) of 91.1 (15.2) among controls. The predicted 6.8-point mean difference for Bayley III Cognitive scores is consistent with our observed 6.3-point difference in mean WIDEA scores at 6 months among NEATO subjects. Predicted Bayley III Cognitive distributions lead to an expected 25.1% of subjects with a cognitive score of < 90 among Epo treated subjects, and 47.1% among controls.

Incorporating expected death rates of 12% and 14% respectively for Epo treated and controls leads to an expected primary outcome rate of 34.1% among treated and 54.5% among controls (**Table 3**). We acknowledge that our primary outcome is based on both Bayley III Cognitive scores, and clinical assessments of CP and GMFCS level, but expect Bayley status to be the major case indicator.

In addition, Cheong et al. evaluated the correlation between MRI findings obtained within 10 days of birth and 2-year clinical status outcomes for participants in the ICE trial (Infant Cooling Evaluation). Specifically, basal ganglia and thalamus (BGT) injuries were classified as abnormal if moderate/severe abnormalities were noted on T1- and T2-weighted images. In our phase II trial, we find only 4.5% (1/22) among Epo treated subjects have BGT injury as compared to 20% (5/25) among control subjects. Cheong et al. estimates that the probability of death/NDI at two years is 88% (PPV) for BGT abnormal subjects as compared to 32% (1-NPV) for BGT normal subjects.

Applying these rates to our phase II BGT results yields **expected death/NDI rates of 34.5% among Epo treated**, and 43.2% among controls. For the ICE trial, the overall death/NDI rate for ICE hypothermia subjects was 51%, which is approximately the same as our expected control rate. Therefore, based on animal data, phase I data, and projections from phase II data we expect primary outcome rates from 31-35% among Epo treated subjects with a protective relative risk of 0.65 to 0.71.

### 7.1.4 Power and Sample Size for Primary Outcome

In order to determine the necessary sample size for efficacy evaluation we need to formulate assumptions for the primary outcome rate in the Epo treated and control groups. The primary outcome measure is the composite rate of death or NDI, and current cohort studies suggest that the primary outcome occurs among 49% of infants treated with hypothermia alone (standard of care). Based on human data presented in Rogers et al. (2014), animal studies including Traudt et al., and the NEATO phase II data we assume that 33% of treated infants will die or have NDI, corresponding to a relative risk of 0.67. Assuming an intervention rate of 33% yields greater than 90% power, while we have 88% power for an alternative of 34% (**Table 4**). In order to compute power, we assume a 90% follow-up rate with n=225/250 subjects evaluated in each arm.

**Table 4. Power analysis for the primary outcome assuming n=500 patients randomized and 10% loss to follow-up**

Control	Intervention	Relative Risk	Power
49%	32%	0.65	95%
49%	33%	0.67	92%

49%	34%	0.69	88%
49%	35%	0.71	83%

## 7.2 Sample size for efficacy secondary outcomes

Our key secondary long-term outcome is an ordered categorical 24-month status measure that classifies subjects as: dead; moderate or severe impairment; mild impairment; and normal. Use of this measure allows a detailed assessment of potential shifts in the distribution of outcomes toward improved status associated with treatment. Statistical analysis of this outcome will use a generalization of the Wilcoxon test that controls for recruitment site and HIE severity. Regression models for ordered categorical outcomes can also be used to provide adjusted treatment effect estimates.

To consider power we have used 2013 data from three large sites participating in the phase II trial (UCSF, Wash U, CNMC) to estimate the distribution of outcomes within the control group. We calculate power for the stratified Wilcoxon test assuming a set of alternatives that are consistent with the assumption of a 33% rate of death or impairment (Scenarios 1 and 2, **Table 5**) or a 32% rate (Scenarios 3 and 4, **Table 5**) associated with intervention that was used to power the primary analysis. We assume a small effect on the death rate, and compute power for alternative shifts in the distribution of outcomes. For example, in Scenario 1 we assume no reduction in the death rate, and an 8% reduction in the moderate/severe category (relative risk = 0.55), and an 8% reduction in the rate of mild impairment (relative risk = 0.50) which yields 81% power using a two-sided alpha=0.05 test. Scenario 3 considers a larger reduction in the rate of moderate/severe and a smaller reduction in the mild category and yields 90% power. Scenarios 3 and 4 consider a 32% overall rate of impairment or death and yield 90% or greater power. Therefore, our study is adequately powered to detect modest but clinically important shifts in the outcome distribution.

**Table 5. Power analysis for a four-level outcome measure with n=500 patients randomized and assuming 10% loss to follow-up**

	Neurodevelopmental Impairment			Mortality	Power
	Normal	Mild	Moderate/Severe		
Placebo Arm	51%	17%	18%	14%	--
Epo Arm					
Scenario 1	67%	9%	10%	14%	81%
Scenario 2	67%	11%	10%	12%	86%
Scenario 3	68%	9%	9%	14%	86%
Scenario 4	68%	11%	9%	12%	92%

Given the a priori hypothesis that treatment effect may differ according to gender or HIE severity we will conduct a pair of subgroup analyses that assesses treatment effects separately for males and for females, and separately for moderate and severe HIE. Subgroup specific treatment effects will be computed and inference will be based on a single Covariate-by-Treatment test for interaction using logistic regression.

## 7.3 Sample size for MRI/MRS biomarkers

For imaging measures, we will have data for all subjects. Assuming a 10% missing data rate we have 80% power to detect a difference in the mean of secondary outcomes across treatment groups of 0.26 SDs. For the inflammation and brain injury biomarkers, we will have a total of 200 subjects and have 80% power to detect a mean difference across the treatment groups of 0.4 SDs.

## 7.4 Sample size for plasma biomarkers of brain injury and inflammation

A sample size of 91 neonates per group would have been required to detect a 0.5 SD difference on the log scale with a single observation per neonate with 80% power while controlling for a Type I error of 0.0125 (4 markers, Bonferroni). However, since we have 4 samples per neonate, a sample size of 100 neonates per treatment group (with correlated 400 samples per group) will be more than sufficient to attain >80% power.

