Objectives	
1) To determine if 5 doses of Epo 1000 U/kg (birth weight) intravenous (IV) reduces the rate of death or neurodevelopmental impairment (mild, moderate, or severe) at 24 months of age.
 
2) To assess safety of Epo.
 
3) To determine whether Epo decreases the severity of HIE-induced brain injury as evidenced by early MRI and plasma biomarkers of brain injury.

Design	Prospective, randomized, double-masked, placebo-controlled study
Arms	
Treatment: Hypothermia (standard of care) plus Epo
 
Placebo: Hypothermia (standard of care) plus normal saline

Procedures	
 - Screen all cooled infants to evaluate eligibility for HEAL - Determine severity of encephalopathy using modified Sarnat exam - Consent and randomize patients - Randomized subjects receive five doses of either study drug or placebo - First dose administered within 24+2 hours of age (Study Day 1); subsequent doses given at the same time of day on Study Days 2, 3, 4, and 7 - Brain MRI and MR spectroscopy ideally performed between 96 and 144 hours post-birth, as part of routine clinical care - Blood collected prior to administration of first study drug dose, and on Study Days 2 and 4 (3 samples total, 1.5 mL each) - Urine (2 samples) collected on Study Days 0-1, and after completion of rewarming on Study Days 3-4 - Phone follow-up at 4, 8, 12, 18, and 24 months: parental questionnaires regarding intervening medical and developmental history, and developmental milestones (Warner Initial Developmental Evaluation of Adaptive and Functional Skills (WIDEA), 12, 18, and 24 months only); All phone interviews may be done in person if desired - 24-month in-clinic evaluation includes a standardized neurologic exam, Bayley III, Gross Motor Function Classification System (GMFCS) evaluation, Child Behavior Checklist (CBCL), and growth parameters. For extenuating circumstances, for example, COVID-19 restrictions, the in-person elements of the final endpoint evaluation may be performed up to 36 months of age. - Extended contact phone calls every 6 months from 2.5 through 8 years of age (WIDEA at 30 and 36 months)
Sites	At least 15, and up to 30 centers in the United States

TABLE OF CONTENTS

SYNOPSIS.....	8
1 STUDY OBJECTIVES	9
1.1 SPECIFIC AIMS.....	9
1.1.1 Aim 1: Efficacy	9
1.1.2 Aim 2: Safety	9
1.1.3 AIM 3: Biomarkers of Neonatal Brain Injury	10
1.2 ENDPOINTS.....	10
1.3 OVERVIEW OF STUDY DESIGN	10

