1.3 OVERVIEW OF STUDY DESIGN

1.3.1 Definition of Study Day

To ensure study procedures are consistent across sites, the following definition will be used:

Study Day: Study Day 1 is defined as the calendar day on which Intervention 1 (first administration of study drug) occurs. If the study drug is first administered on the calendar day following the day of birth, then the day of birth will be called Study Day 0.

We propose a multicenter, randomized, double-masked, placebo-controlled Phase III clinical trial. We will enroll 500 infants at a minimum of 15, and a maximum of 30 sites. Patients will be randomized to receive either IV Epo 1000 U/kg/dose based on birth weight, or an equal volume of IV normal saline (NS). Study drug will be administered on study days 1, 2, 3, 4, and 7. All enrolled infants will receive standard clinical care including 72 hours of therapeutic hypothermia. The initial neonatal intervention and safety monitoring will begin at time of study consent (prior to 24 hours of age), and will be continued to hospital discharge. Follow-up evaluations will be performed at 4, 8, 12, 18, and 24 months via phone questionnaire, and at 24 months via in person neurodevelopmental examination.

Primary endpoint at age 24 months \pm 56 days (i.e., \pm 2 months) will be determined by presence of death or neurodevelopmental impairment.

Blood samples will be obtained from *all subjects* at 3 time points: baseline, Study Day 2, and Study Day 4. Urine samples will be obtained from *all subjects* at 2 time points: after consent on Study Day 0-1, and after completion of rewarming on Study Day 3-4. We will measure a baseline plasma Epo concentration prior to the administration of the first study drug dose. A subset of 200 patients identified post-hoc after meeting pre-defined criteria for quality of MRI/MRS data will have their samples measured for circulating and urinary biomarkers of brain injury and inflammation. All infants will have a brain MRI and MRS, ideally between 96 and 144 hours post-birth, as part of the standard clinical management of cooled infants. The study neuroradiologists will perform masked centralized reading of these neonatal brain MRI and MRS scans.

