6 CLINICAL AND LABORATORY EVALUATIONS

6.1 SCHEDULE OF EVALUATIONS

Table 3. Schedule of Evaluations

Evaluation	Visit Day	Window	Location	Details
Screening	Study Day 0 or 1	Before randomization	NICU	Screening Clinical Assessment (Apgar, resuscitation, acidosis, Modified Sarnat exam, Inclusion/Exclusion assessment)
Therapeutic Hypothermia Begins	Study Day 0 or 1	Begin by <6 hours post-birth	NICU	Begins prior to administration of study drug and at <6 hours of age, continues for 72 hours, per standard of care.
Consent & Enrollment	Study Day 0 or 1	Prior to 24 + 2 hours post-birth	NICU	Informed Consent
Randomization	Study Day 0 or 1	Prior to 24 + 2 hours post-birth	Pharmacy	HEAL Portal
Blood sample (pre-intervention)	Study Day 0 or 1	Before Intervention 1	NICU	1.5 mL blood sample
Urine sample 1	Study Day 0 or 1	1 st void after consent	NICU	1-2 mL urine sample, ideally obtained prior to study drug administration (note: urine may be collected after study drug administration if not available earlier, and in this case, does not require a Protocol Deviation)
Intervention 1 (study drug)*	Study Day 1	Prior to 24 + 2 hours post-birth	NICU	Target time is as soon as possible
Intervention 2 (study drug)	Study Day 2	24 ± 2 hours following Intervention 1	NICU	Target time is same time of day as Intervention 1
Blood sample 2	Study Day 2	24 ± 2 hours following Intervention 1	NICU	1.5 mL blood sample. Target time is same time of day as Intervention 2
Intervention 3 (study drug)	Study Day 3	48 ± 2 hours following Intervention 1	NICU	Target time is same time of day as Intervention 1
Urine sample 2	Study Day 3-4	After rewarming completed, and within 24 hours after rewarming	NICU	1-2 mL urine sample

Evaluation	Visit Day	Window	Location	Details
Intervention 4 (study drug)	Study Day 4	72 ± 2 hours following Intervention 1	NICU	Target time is same time of day as Intervention 1
Blood sample 3	Study Day 4	72 ± 2 hours following Intervention 1	NICU	1.5 mL blood sample. Target time is same time of day as Intervention 4
Brain MRI/MRS (routine clinical care)	Study Day 4-5	Ideally between 96-144 hours post-birth	NICU	After rewarming, and ideally after Intervention 4 has been administered
Clinical assessment	Study Day 5	Anytime this calendar day	NICU	Modified Sarnat exam
Intervention 5 (study drug)	Study Day 7	144 ± 2 hours following Intervention 1	NICU	Target time is same time of day as Intervention 1
EEG Summary	Study Days 1-7	N/A	NICU	Upload EEG reports

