6.3.5 Plasma and urine biomarkers; baseline Epo measurement

Three blood samples (1.5 mL each) will be collected in EDTA tubes from each enrolled patient over the course of their hospital stay to be used to study circulating biomarkers of inflammation and brain injury. The first blood sample (collected prior to the administration of study drug) will also be used to measure a baseline Epo level. A baseline Epo level may be helpful to determine the chronicity of hypoxic-ischemic stress *in utero*, a potential confounder of the relationship between Epo therapy and 2-year outcome. Additional samples are collected on Study Days 2 and 4.

Samples may be refrigerated for up to 4 hours prior to processing and freezing. As soon as possible after drawing, samples should be spun for 8 min at 2000 G, plasma removed into a separate container, and plasma and pellet stored in labeled tubes at -70°C or below. RNALater will be added to one pellet to preserve RNA for future studies. Please refer to the Laboratory SOP for further details. Plasma Epo concentrations will be measured in duplicate using Meso Scale Discovery (MSD) technology at the UW Laboratory Core.

We will assay blood samples for circulating biomarkers of brain injury and inflammation in a subset of infants (N = 200; 100 treated and 100 control infants with balanced numbers of moderate and severe HIE. These subjects will all have MRI scans that have met pre-defined acceptance criteria). We will assay putative biomarkers of brain injury severity in neonates including: S100B, glial fibrillary acidic protein (GFAP), Tau, neuron-specific enolase (NSE), and ubiquitin C-terminal hydrolase-L1 (UCH-L1). Given the role of inflammation in HIE, we will also measure the following inflammatory markers: interleukin (IL)-1beta (β), IL-6, IL-8, and tumor necrosis factor-alpha (TNF-α). All samples will be run in duplicate using MSD technology in the UW core laboratory. This combination of factors will allow us to evaluate the subject's inflammatory

state over time, provide insight as to the timing and severity of brain injury, and potentially, provide insight as to why some individuals might respond more optimally to Epo.¹²⁴⁻¹²⁷

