## 5.7 Circulating Biomarkers

Inflammation is thought to play an important role in HIE and CP. Biomarkers of inflammation that we measure include: interleukin (IL)-1 $\beta$ , IL-6 and IL-8 and TNF- $\alpha$ . Putative biomarkers of brain injury in neonatal HIE include: glial fibrillary acidic protein (GFAP), ubiquitin C-terminal hydrolase-L1 (UCH-L1), S100B, Tau, and neuron-specific enolase (NSE). We will select a random subset of 200 subjects (100 treated and 100 controls with each group, for example, including both moderate and severe HIE) to measure circulating biomarkers of inflammation and brain injury. We will collect 3 plasma samples from each infant at the following time points based on hour of age: < 24 hours; Study Day 2; Study Day 4. Our analysis will focus on time-specific comparisons of the mean biomarker measure across treatment

groups using appropriate regression methods while controlling for site and HIE severity. In addition, we will conduct longitudinal analysis using linear mixed models that permit an omnibus test across all four measurement times and allow inference on differential rates of change across treatment groups.

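### The biomarker power argument and the mixed model count four plasma samples per infant, but the trial draws three, only two of them after dosing; the pre-dose value is not named as a covariate

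*SAP*

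**What the plan says.** **Power text.** SAP 7.4 starts from 91 infants per group: 0.5 SD on the log scale, one observation each, 80% power, level 0.0125 (Bonferroni for four markers). It then argues that 100 per group is more than enough: "However, since we have 4 samples per neonate, a sample size of 100 neonates per treatment group (with correlated 400 samples per group". Protocol 9.4.4 says the same.

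**Analysis text.** SAP 5.7 states "We will collect 3 plasma samples from each infant". A few lines later it describes linear mixed models that allow "an omnibus test across all four measurement times". Protocol 9.3.5 has the same pair of statements. The time-specific group comparisons are to be made "using appropriate regression methods while controlling for site and HIE severity".

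**Schedule.** The protocol synopsis gives a draw before the first dose "and on Study Days 2 and 4 (3 samples total, 1.5 mL each". The overview of study design (Protocol 1.3.1) has blood taken "at 3 time points: baseline, Study Day 2, and Study Day 4". In the Protocol 6.1 table the last draw, blood sample 3, falls on Study Day 4: "1.5 mL blood sample. Target time is same time of day as Intervention 4". Protocol 6.3.5 confirms that the first draw is pre-dose: "The first blood sample (collected prior to the administration of study drug".

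**Status.** SAP 4 and Protocol 1.2 class the circulating biomarkers as exploratory.

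**The concern.** The sample count in the power sentence contradicts the schedule, and SAP 5.7 contradicts itself within one paragraph. No fourth plasma draw appears anywhere, and the two urine samples are banked for future studies, so they cannot supply it. The first of the three draws precedes study drug, so it cannot carry a treatment effect. Counting it as one more replicate overstates the information on the drug.

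That same draw has a better use. It is scheduled for every infant and is the natural baseline covariate, yet the time-specific comparisons name only site and HIE severity. SAP 5.6, just before, adjusts the routine laboratory tests for their baseline value.

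At stake are the stated justification for the 200-infant biomarker subset and the efficiency of Aim 3b.

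**Working it through.** **Inputs from the documents.** Effect 0.5 SD on the log scale; level 0.0125, taken as two-sided; 100 infants per group; one pre-dose and two post-dose draws. **Assumed, because the documents give none:** the correlation between the two post-dose draws (0.3 to 0.9) and between pre- and post-dose values (0.2 to 0.7). The level applies at each time point.

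**1. The plan's own figure.** For a two-sample comparison of means, n per group = 2(z₁₋α/₂ + z₀.₈)²/d² = 2(2.498 + 0.842)²/0.25 = 89.2, so 90. The noncentral t solution is 90.78, so 91, which matches. A one-sided level would give 77 and does not match.

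**2. Sample count.** 3 × 100 = 300 per group, against 400 stated. Post-dose: 2 × 100 = 200.

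**3. One draw.** The noncentrality is 0.5 × √(100/2) = 3.54. Power by noncentral t is 84.4% at 100 per group, 80.1% at 91 and 79.6% at 90.

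**4. Mean of m draws.** With equal correlation ρ, the variance of an infant's mean relative to one draw is (1 + (m − 1)ρ)/m. For two post-dose draws this is (1 + ρ)/2. The calculation takes the 0.5 SD effect to be present at every draw averaged. Power at 100 per group (normal approximation):

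| ρ | two post-dose draws | four draws, as the power text counts them |
|---|---|---|
| 0.3 | 97.0% | 99.6% |
| 0.5 | 94.3% | 97.6% |
| 0.7 | 90.9% | 93.6% |
| 0.9 | 87.1% | 88.1% |

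The miscount costs 1 to 3 percentage points and leaves power above 80% throughout.

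**5. Why the pre-dose draw must not be averaged in.** A simple mean of all three draws would dilute the effect to 0.5 × 2/3 = 0.33 SD, with variance (1 + 2ρ)/3. Power would then be 77%, 65%, 56% and 48% for ρ = 0.3, 0.5, 0.7 and 0.9. The plan does not propose this analysis. It shows why a corrected power sentence should count two draws rather than three.

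**6. Pre-dose value as covariate, one post-dose time.** The residual variance falls by the factor 1 − ρ², so the effect becomes 0.5/√(1 − ρ²) SD (197 degrees of freedom). For pre/post correlations of 0.2, 0.3, 0.5 and 0.7, power is 86%, 88%, 94% and 99%, against 84% without it.

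**7. The neighbouring power figure.** SAP 7.3 and Protocol 9.4.3 give 80% power at 0.4 SD with 200 subjects and state no level. This reproduces at two-sided 0.05 (80.4%) but not at 0.0125 (62%).

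**The case against.** The other side can fairly say that the four is an editorial slip. Every operational section says three draws, the mixed model runs on three times without change, and the power conclusion stands. All of that is correct, and it keeps the point small.

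Three stronger readings are tempting, and the documents do not support them:

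- *The biomarker comparisons are underpowered.* They are not on the plan's own terms: one draw already gives 84%. A figure below 80% at full enrolment appears only if all nine listed markers are treated as one Bonferroni family (0.05/9, 77% with one draw), and the plan does not say that.
- *The five brain-injury markers have no power statement, or the 0.0125 level leaves them unprotected.* SAP 7.3 and Protocol 9.4.3 give 80% power at 0.4 SD for inflammation and brain-injury markers alike. The 0.0125 level appears only in the sample-size text, as a planning input; the analysis sections set no testing level for these markers. The four inflammatory markers fit the count. Not naming them is missing detail for an exploratory outcome.
- *The plan ignores the pre-dose value.* It does not exclude it. The mixed model spans the measurement times and so uses that draw, and the reference to suitable regression methods leaves room for a covariate. Naming it is an improvement rather than the correction of an error. SAP 5.6 concerns routine laboratory tests, so the difference is not a contradiction.

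One might also rest the power claim on the single draw alone. The margin is thin: Protocol 7.6.2 foresees missed blood collections, and at 90 evaluable infants per group single-draw power is 79.6%. The repeated-sample argument is therefore worth correcting rather than dropping.

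**Conclusion.** The contradiction is real and stands in the current text of both documents: four samples or times in SAP 5.7 and 7.4 and Protocol 9.3.5 and 9.4.4, against three scheduled draws. The correct count is 300 samples per group, 200 of them post-dose.

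The conclusion of more than 80% power for 0.5 SD at 0.0125 survives, with 84% from one draw if all 100 infants per group are evaluable. The 87% to 97% for two post-dose draws rests on the assumed correlations and on the effect being present on both days. The covariate gain likewise depends on an unknown pre/post correlation and is only about two points if that is 0.2.

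This is worth correcting but minor. It touches exploratory outcomes only.

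**What to change.** 1. In SAP 5.7 and 7.4 and Protocol 9.3.5 and 9.4.4, change four samples and four times to three, and 400 samples per group to 300, of which 200 are post-dose. Restate the power argument on the two post-dose draws with the assumed correlation stated. Give the single-draw 84% as the floor if all 100 per group are evaluable, and note 79.6% at 90.
2. In SAP 5.7 and Protocol 9.3.5, adjust the Day 2 and Day 4 comparisons of log values for the log pre-dose value as well as site and HIE severity. Keep infants without a pre-dose sample through the planned mixed model.
3. Optional clarification: say which four markers the 0.0125 planning level refers to, and have the sponsor confirm the level behind the 0.4 SD figure in SAP 7.3 and Protocol 9.4.3. The 0.05 above is back-calculated.

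The cost is wording and one named covariate, with no new samples or data. The downside of the covariate is negligible: one degree of freedom, and little gain if the pre/post correlation is low.
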